#### 9.2.3. Dose Reductions for Renal Impairment

Because the impact of renal dysfunction on Selinexor is not known, patients with GFR <30mL/min are not eligible to enter the study. Refer to dose adjustment guidelines below for renal dysfunction that develops while on study and unrelated to Selinexor.

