Efficacy Assessment	Efficacy will be assessed by evaluation of bone marrow as pirates and biopsies, complete blood counts, and transfusion records. Hematologic Improvement will be assessed continuously, with the use of CBC values and transfusion records. At the time of bone marrow aspirates and biopsies, full efficacy evaluations will be performed, taking into account blood and bone marrow parameters, and responses will be assessed using the 2006 Modified MDS International Working Group Response Criteria.
Safety Variables & Analysis:	The safety and tolerability of Selinexor and ST will be evaluated by means of drug related AE reports, physical examinations, and laboratory safety evaluations. Common Terminology Criteria for Adverse Events (CTCAE) V4.03 will be used for grading of AEs. Investigators will provide their assessment of causality as 1) unrelated, 2) possibly related, or 3) probably or definitely related for all AEs.
Statistical Analysis:	Primary endpoint evaluation
	The primary endpoint of this study is to investigate the efficacy of Selinexor in patients with MDS refractory to hypomethylating agents (decitabine and/or 5-azacytidine). The standard treatment in this setting is supportive care, where the response rate is assumed to be zero. Therefore, in this population, a response rate of 25% would be considered promising, whereas a 5% response rate would not be considered promising. For purposes of assessing the primary endpoint, response categories will include CR, PR, marrow CR (mCR), or Hematologic Improvement. Using a Simon's two-stage minimax design, this trial will accrue a maximum of 20 patients who receive study drug. Early termination may occur if no responses are observed in the first 13 patients. If at least one response is observed, the trial will continue to the maximum sample size. At the end of the trial, the treatment strategy will be considered promising in this patient population if at least 3 patients achieve a response. The type I and type II errors are set at 0.10.  The response evaluation cohort will include those patients who have completed one cycle of therapy and have undergone at least one full scheduled post-treatment disease assessment (informative bone marrow aspirate or biopsy, cytogenetics, and

Memorial Sloan Kettering Cancer Center IRB Number: 14-005 A(17)

Approval date: 25-Jan-2021

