# 9.2.2. Dose Modifications for Hematologic and Non-hematologic Toxicities Related to Selinexor

The criteria for dose modification for toxicities at least possibly related to selinexor are outlined below in Table 1. Supportive care guidelines for management of selinexor-related toxicities and indications for dose modifications are described in Table 2.

Table 1. Pre-specified Dose Modifications for AEs Related to Study Drug

	Dose Level		
Starting Dose	1	60mg	twice weekly
Dose Reductions	-1	40 mg	twice weekly
	-2	40 mg	once weekly

Table 2. Supportive Care and Dose Modification Guidelines

Toxicity and Intensity	Supportive treatment	Selinexor Dose Modification
Fatigue (common)		
Grade 1	Rule out other causes of fatigue. Consider addition of 4-8 mg dexamethasone or equivalent on the day after selinexor. Insure adequate caloric intake and assess volume status.	Maintain dose.
Grade 2	Rule out other causes of fatigue. Consider addition of 4-8 mg dexamethasone or equivalent on the day after selinexor. Insure adequate caloric intake and assess volume status. For additional support see NCCN fatigue guidelines.	Maintain dose. Consult medical monitor for additional option such as temporarydose reduction or short dose interruptions.
Grade 3	See above guidelines for Grade 2 fatigue	Interrupt selinexor dosing until resolved to Grade ≤ 2, For first occurrence of Grade 3, if adequate supportive care resulted in fatigue improving to Grade ≤ 1 within 7 days, restart selinexor at current dose. Otherwise, restart selinexor one dose level lower
Anorexia or Weight loss		
Grade 1	Rule out other causes of anorexia. Assess dietaryoptions (e.g., try a variety of other foods). Add high-calorie supplements (e.g., Ensure®). Consider addition of 4-8 mg dexamethasone or equivalent on the day after selinexor dosing.	Maintain dose.
Grade 2	Rule out other causes of anorexia.  Assess dietaryoptions (e.g., try a variety of other foods).  Add high-calorie supplements (e.g., Ensure®).  Consider addition of 4-8 mg dexamethasone or equivalent on the day after selinexor.  Consider megesterol acetate 80-400 mg daily.  Consider anabolic steroids such as oxandrolone, or dronabinol (Marinol®) or other cannabinoid, mainlyfor patients who cannot tolerate steroids or are at high risk to progress.  For additional supportive care see NCCN guidelines (see Appendix 8).	Selinexor may be skipped intermittently while supportive medications are instituted, usuallyfor < 1 week.

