Grade 4 Thrombocytopenia Without bleeding	Follow guidelines (above) for Grade 3 thrombocytopenia without bleeding. Transfuse as per institutional guidelines.	In general, hold selinexor dos until platelet counts >50,000/mm³ or baseline, then resume selinexor dosing at one dose level lower (See Table 1). In certain cases when there is significant disease involvement in the bone marrow (e.g., in heavily pretreated multiple myeloma) or pre-existing compromised marrow function (e.g., due to prior marrow-toxic therapy), the Investigator in consultation with the Sponsor may decide to continue Selinexor dosing, provided that platelet counts and bleeding symptoms/signs are closelymonitored.
≥ Grade 3 Thrombocytopenia with bleeding	Transfuse as per institutional guidelines. Follow guidelines for Grade 3 thrombocytopenia without bleeding.	Hold selinexor dosing until platelet counts >50,000/ mm  or baseline, then resume selinexor dosing at one dose level below (See Table 1)
Neutropenia		
Grade 3 Neutropenia without fever	Implement growth factors per institutional guidelines until neutrophils are consistently > 1,500/mm  .	Maintain dose.

Toxicity and Intensity	Supportive treatment	Selinexor Dose Modification
Grade 4 Neutropenia without fever	Implement growth factors per institutional guidelines.	Reduce selinexor dose byone level (See Table 1).  After implementation of growth factors, for patients who achieve neutrophil levels > 1,500/mm³ for > 4 weeks (in the presence or absence of growth factors), selinexor dose maybe re-escalated, with frequent monitoring implemented.
Grade 3 or 4 Neutropenia with fever (febrile neutropenia)	Implement growth factors per institutional guidelines. Implement broad anti-microbial coverage per institutional guidelines. Please note that selinexor has not been associated to date with any opportunistic infections	Hold selinexor until fever resolves and patient is clinicallystable. When patient is clinically stable, restart dosing one dose level lower (See Table 1) After implementation of growth factors, for patients who achieve neutrophil levels >1,500/mm³for >4 weeks, selinexor dose may be re-escalated, provided frequent monitoring is implemented.
Other Selinexor-related A	dverse Events d	
Grade 1 or 2	Initiate standard supportive care per institutional guidelines.	Maintain dose.

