Grade 3	Initiate standard supportive care and follow institutional guidelines.	Delay dose until resolved to Grade ≤ 1 or baseline, then reduce by one dose level (See Table 1)
Grade 4	Initiate standard supportive care and follow institutional guidelines.	Delay dose until resolved to Grade ≤ 1 or baseline, then reduce by two dose levels (See Table 1)

All dose modifications should be based on the worst preceding toxicity.

<sup>a National Comprehensive Cancer Network®. NCCN Clinical Practice Guidelines in Oncology(NCCN Guidelines®): Fatigue. Available at http://www.nccn.org/professionals/physician\_gls/pdf/fatigue.pdf

<sup>b Benson AB, Ajani JA, Catalano RB, et al. Recommended guidelines for the treatment of cancer treatment-induced diarrhea. J Clin Onc 2004; 22:2918.

 $^{\rm c}$  Isolated values of  $\geq$  Grade 3 alkaline phosphatase values will NOT require dose interruption. Determination of liver vs. bone etiology should be made, and evaluation of gamma-glutamyl transferase (GGT), 5'-nucleotidase (5'NT), or other liver enzymes should be performed.

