#### Dose Adjustment Guideline for renal dysfunction while on study

Renal Dysfunction	Recommended Action
Normal to Moderate (GFR ≥ 30 mL/min)	Full dose
Severe (GFR < 30 mL/min)	
 
Reduce Selinexor by 30% for at least two weeks
 
If reduced dose is well tolerated, or GFR increases to >30mL/min, then Selinexor may be increased to starting dose after consultation with the Principal Investigator.
 

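### Section 9.2.3 limits its GFR <30 dose cut to renal dysfunction unrelated to selinexor, so a possibly related fall, if recorded as Grade 1-2, has no written reduction

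*Combined protocol and SAP*

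**What the plan says.** Section 9.2.3 gives its reason first: "Because the impact of renal dysfunction on Selinexor is not known, patients with GFR <30mL/min are not eligible to enter the study". The next sentence introduces the on-study guideline and limits it: "Refer to dose adjustment guidelines below for renal dysfunction that develops while on study and unrelated to Selinexor". Under that guideline, GFR below 30 mL/min leads to this action: "Reduce Selinexor by 30% for at least two weeks". If the lower dose is tolerated, or GFR recovers above 30, "then Selinexor may be increased to starting dose after consultation with the Principal Investigator".

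Attribution therefore decides which rule applies. The Synopsis defines the categories: "Investigators will provide their assessment of causality as 1) unrelated, 2) possibly related, or 3) probably or definitely related for all AEs". Section 9.2.2 takes two of the three: "The criteria for dose modification for toxicities at least possibly related to selinexor are outlined below in Table 1". Its Table 2 has rows for fatigue, anorexia or weight loss, nausea, hyponatremia, diarrhea, thrombocytopenia and neutropenia, but none for creatinine, GFR or renal function. A related renal event falls to the row for other selinexor-related events. At Grade 1 or 2 that row says "Initiate standard supportive care per institutional guidelines" and keeps the dose as it is. At Grade 3 it says "Delay dose until resolved to Grade ≤ 1 or baseline, then reduce by one dose level (See Table 1"). At Grade 4 it requires a delay and a two-level reduction.

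**The concern.** The stated reason concerns what poor renal function does to the handling of selinexor. That uncertainty is the same whether the kidney was injured by infection, by dehydration or by the drug. Limiting the guideline to unrelated cases therefore does not follow from its own rationale. For an event recorded as Grade 1-2, suspecting the drug leads to a weaker written action than clearing it.

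A possibly related call is realistic. Section 11 lists increased creatinine among the occasional side effects of selinexor, with dehydration in the same list. What is at stake is dosing safety in an individual patient, not inference from the trial.

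**Working it through.** The plan gives no figure of its own on this point. The check sets the rules side by side, then sizes the difference.

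**Step 1. Written action for a fall below 30 mL/min**

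| Attribution | Recorded grade | Source | Written action |
|---|---|---|---|
| Unrelated | Any | 9.2.3 | 30% cut, at least two weeks |
| Unrelated | 3 or higher | 9.2.1, as well as 9.2.3 | Hold for up to 28 days, then resume at the same dose if resolved |
| At least possibly related | 1-2 | 9.2.2, Table 2, other events | Dose unchanged, supportive care |
| At least possibly related | 3 | Same row group | Delay, then one level down |
| At least possibly related | 4 | Same row group | Delay, then two levels down |

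The third line is the gap. The second line shows a separate overlap: an unrelated event of Grade 3 or higher meets both a hold and a 30% cut, and neither is given precedence.

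**Step 2. Dose difference between the first and third lines**

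Inputs: 60 mg twice weekly, two weeks on and one off, four doses per 21-day cycle (Section 9.1.1); lower levels of 40 mg twice weekly and 40 mg once weekly (Table 1); 30% cut (Section 9.2.3). A 14-day window contains 2 to 4 doses on the twice-weekly schedule, depending on where the off week falls.

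- 60 mg twice weekly: 60 × 0.70 = 42 mg, a difference of 18 mg per dose. Per window, 2 × 18 = 36 to 4 × 18 = 72 mg. Against the cycle dose of 4 × 60 = 240 mg, that is 15% to 30%.
- 40 mg twice weekly: 40 × 0.70 = 28 mg, a difference of 12 mg per dose and 24 to 48 mg per window. Against 160 mg, again 15% to 30%.
- 40 mg once weekly, assuming the same off week: 12 mg per dose with 1 to 2 doses per window, so 12 to 24 mg. Against 80 mg, again 15% to 30%.

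These are nominal doses. Tablets come as 10 and 25 mg, or as 20 mg (Section 5.1), so 42 and 28 mg would have to be rounded.

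**Step 3. How far creatinine must rise to cross the line**

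The inclusion criteria admit patients from an estimated clearance of 30 mL/min by Cockcroft-Gault. With age, weight and sex fixed, clearance is inversely proportional to creatinine, so the multiple that brings baseline B down to 30 is B/30.

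| Baseline clearance (mL/min) | Creatinine multiple |
|---|---|
| 35 | 35/30 = 1.17 |
| 40 | 40/30 = 1.33 |
| 45 | 45/30 = 1.50 |
| 60 | 60/30 = 2.00 |
| 90 | 90/30 = 3.00 |

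A modest rise can take an eligible patient with low baseline clearance below 30. This treats estimated clearance and the GFR in Section 9.2.3 as the same quantity. The documents do not say which grade such a rise would receive.

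**The case against.** The strongest reply is that the weak branch has not been shown to occur. Grading follows CTCAE 4.03, whose cut-offs the documents do not reproduce. If a GFR below 30 is recorded as Grade 3 or 4, Table 2 already requires a delay and a reduction, which is stricter than a 30% cut. This stands, and it is why the point is conditional.

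Other safeguards exist. Section 9.2.7 requires consultation with the Principal Investigator on dose changes, Section 10.0 requires investigator review of chemistry before cycle 1 dosing, and Section 16 has the Principal Investigator assess laboratory toxicities. In a single-center study these reduce the practical risk. None sets a GFR trigger, and Section 9.2.7 attaches to a change in dose, which the Grade 1-2 row does not call for. Under Section 9.2 a concurrent toxicity of higher grade would govern, but only if there is one. The guideline table itself carries no attribution limit, so staff might apply it to every case; the sentence that introduces it says otherwise. The row for other events carries a footnote marker d whose text is not in the copy reviewed, so a qualifier there cannot be excluded.

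Two stronger readings are tempting. A reader might infer that a suspected drug-related fall could have no written action at all, because a laboratory value is not automatically an adverse event. Section 11 does count a value that leads to a dose change or that the investigator considers clinically significant, and a fall into the protocol's own severe category would very plausibly qualify. A reader might also apply the listed 4 to 20 per 100 to 20 patients and conclude that 0.8 to 4 are affected. That range covers any creatinine increase, not falls below 30, so it does not size the gap.

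**Conclusion.** The scope of Section 9.2.3 does not match its stated reason, and that mismatch holds whatever the grade. The weaker action follows only if a fall below 30 is judged at least possibly related and recorded as Grade 1-2. In that case the written difference at the starting dose is 18 mg per dose, or 36 to 72 mg over a two-week window.

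The number of patients affected is unknown and may be zero. The KCP-330-002 toxicity table lists two creatinine increases, both Grade 1, and Section 3.2 reports no clinically significant renal dysfunction in phase 1. The rule is also only a short caution: Section 9.2.3 allows a return to the starting dose with GFR still below 30 if the reduced dose was tolerated.

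A reader might infer that the protocol removes renal protection whenever the drug is suspected. The text does not support that, because related Grade 3-4 events are handled more strictly than unrelated ones under Section 9.2.3. This is a wording gap worth an optional correction. It affects no endpoint, sample size or error rate. The conclusion assumes that the introducing sentence governs the table and that footnote d does not alter the row.

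**What to change.** Delete from Section 9.2.3 the closing words that limit the on-study guideline to dysfunction not caused by selinexor. Then add one sentence: *Where 9.2.3 and 9.2.1 or Table 2 both apply, the more restrictive action governs.* Section 9.2.1 has to be named because an unrelated event of Grade 3 or higher otherwise meets both a hold and a 30% cut.

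After the change, a fall below 30 recorded as Grade 1-2 gets the 30% cut whatever its cause, and related Grade 3-4 events stay under the stricter Table 2 action.

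The cost is one deletion and one sentence. No new tests are needed, since chemistry is already done weekly in cycle 1 and every two weeks afterwards (Section 10.0, footnote 4). The downside is a few more short dose reductions. Replacing the 30% cut with a Table 1 level would ease dispensing, but it is a separate trade-off and not part of this fix: at level -1 it would halve the weekly dose (80 to 40 mg), and there is no level below -2.

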#### Dose Adjustment Guideline for renal dysfunction while on study

Renal Dysfunction	Recommended Action
Normal to Moderate (GFR ≥ 30 mL/min)	Full dose
Severe (GFR < 30 mL/min)	
 
Reduce Selinexor by 30% for at least two weeks
 
If reduced dose is well tolerated, or GFR increases to >30mL/min, then Selinexor may be increased to starting dose after consultation with the Principal Investigator.
 

# 9.2.4. Selinexor Dose Adjustment in the Setting of Infection

Patients with active uncontrolled infections should have selinexor treatment withheld until the infection has clinically resolved or is controlled. After the infection is controlled, treatment may continue at the original dose. Missed doses will not be replaced. Patients may continue on antibiotics for prolonged periods while re-initiating their selinexor regimen at the discretion of the investigator but the infection must be *clinically* stabilized prior to restarting selinexor.

For patients with recurrent episodes of complicated febrile neutropenia, follow the guidelines outlined in the table above: "Dose adjustment guidelines for hematologic selinexor-related toxicities".

#### 9.2.5. Conditions Not Requiring Selinexor Dose Reduction

The following conditions are exceptions to the above guidelines. Selinexor does not need to be held in the following cases:

- Grade 3 nausea, vomiting or diarrhea (unless persisting > 3 days with adequate treatment of anti-emetics or anti-diarrheals
- Alopecia of any grade
- Weight loss of less than 20%
- Electrolytes abnormalities that are reversible with oral supplements or brief intravenous infusions.

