Toxicity and Intensity	Supportive treatment	Selinexor Dose Modification
Grade 3	See guidelines for Grade 2 anorexia above	Interrupt dosing with selinexor.
		Restart selinexor at 1 dose level reduction
		(see Table 1) once anorexia resolves to Grade ≤ 2 and patient is clinicallystable.
Grade 4 (anorexia only)	See guidelines for Grade 2 anorexia above	Stop dosing of selinexor.
, ,,		Restart selinexor at 1 dose level reduction
		(see Table 1) only if anorexia resolves to
		Grade ≤ 2, patient is clinically stable other contributing factors have been addressed.
Nausea, Acute (common)		Contributing factors have been addressed.
Grade 1	Ensure adequate caloric intake and assess	Maintain dose.
	volume status.	
	Consider alternate 5-HT3 antagonists and/or D2 antagonists as needed. Consider addition of	
	NK1 antagonists.	
	Consider addition of 4-8 mg dexamethasone or	
0 1 0	equivalent on the day after selinexor.	
Grade 2	See guidelines for Grade 1 nausea above. For additional options see NCCN guidelines for	Selinexor may be skipped intermittently while supportive medications are instituted,
	antiemesis (see Appendix 7).	usuallyfor <1 week.
Grade 3	See guidelines for Grade 1 nausea.	Interrupt selinexor dosing until resolved to
	For additional options see NCCN guidelines for	Grade ≤ 2. For first occurrence of Grade 3,
	antiemesis (see Appendix 7).	if adequate supportive care resulted in nausea improve to Grade ≤ 1 within 3 days,
		restart selinexor at current dose.
		Otherwise, restart selinexor one dose level
		lower (see Table 1). If nausea stabilizes for
		at least 4 weeks at Grade ≤ 1, original dose of selinexor may be resumed.
Hyponatremia (common)		or commencer may be recumed.
Grade 1 (sodium levels <	Ensure that sodium level is corrected for	Maintain dose.
Normal to 130 nM)	hyperglycemia (serum glucose > 150 mmol/L).	
	Rule out other causes of low sodium (e.g., cardiac, hepatic, adrenal, renal and thyroid	
	diseases, SIADH, Fanconi Syndrome,	
	hyperglycemia, diuretic use).	
	Consider salt supplementation 1-2 times per	
Grade 3 (sodium levels	Ensure that sodium level is corrected for	Hold selinexor until Grade ≤ 1 (≥ 130 nM),
126-129 nM) without	hyperglycemia (serum glucose > 150 mmol/L).	restart on the same dose level.
Symptoms	Rule out other causes of low sodium (e.g.,	
	cardiac, hepatic, adrenal, renal and thyroid diseases, SIADH, Fanconi Syndrome,	
	hyperglycemia, diuretic use).	
	Initiate salt supplementation 2-3 times per day.	

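### Section 9.2.5's electrolyte exception, read literally, makes optional the hold that Table 2 requires for asymptomatic Grade 3 hyponatremia (sodium 126-129)

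*Combined protocol and SAP*

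**What the plan says.** Section 9.2.2, Table 2, has its own rows for hyponatremia. For Grade 3 without symptoms (sodium 126-129), the supportive treatment is "Initiate salt supplementation 2-3 times per day" and the dose rule is "Hold selinexor until Grade ≤ 1 (≥ 130 nM"), followed by "restart on the same dose level". The next row covers sodium 120-125, symptomatic Grade 3, and Grade 4. There, sodium is first corrected under the institution's guideline with salt added, selinexor is held, and the dose then drops one level.

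Section 9.2.5 follows Table 2 and opens with "The following conditions are exceptions to the above guidelines", then "Selinexor does not need to be held in the following cases". Its last bullet is "Electrolytes abnormalities that are reversible with oral supplements or brief intravenous infusions". The other bullets state their reach: the gastrointestinal bullet gives a grade and a three-day limit, weight loss is capped at 20%, and alopecia is covered at every grade. The electrolyte bullet is limited only by reversibility.

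**The concern.** Salt by mouth is the treatment Table 2 prescribes in the 126-129 row. If it works, the abnormality was reversible with an oral supplement, and the exception then removes the need for the hold in that same row. Two investigators facing a sodium of 127 could act differently, one holding under Table 2 and the other dosing under Section 9.2.5, each with support in the text.

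What is at stake is dosing through Grade 3 hyponatremia when the drug-specific table says to wait for recovery, and consistency of dosing between patients. It is a matter of safety conduct and does not bear on the efficacy analysis.

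**Working it through.** **Comparing the texts**

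1. *Which rule prevails.* Section 9.2.5 says that it is an exception to what precedes it, and Table 2 precedes it. On a literal reading 9.2.5 wins.
2. *Sodium 126-129, no symptoms.* Table 2: salt, hold to at least 130, same dose on restart. Section 9.2.5: no hold needed if oral supplements reverse it. The overlap is direct, and the two differ only on whether doses are withheld in the meantime.
3. *Sodium 120-125, symptomatic Grade 3, or Grade 4.* Table 2: institutional correction, hold, one-level reduction. Section 9.2.5 reaches this row only if the correction counts as oral supplementation or a brief infusion. That is possible on the words but less plausible clinically.
4. *Other electrolytes.* Hypokalemia and the like have no row of their own and fall under Table 2's general entry for other related events. Here the exception has an obvious use and contradicts no specific row.

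**How many patients**

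Inputs, all from the Phase 1 safety data in Section 3.2 unless stated:
- Solid tumors (KCP-330-002): Grade 3 hyponatremia in 8 patients (16%), described as asymptomatic. Implied denominator 8 / 0.16 = 50.
- AML (KCP-330-001, n = 16): two Grade 1 cases and no Grade 3, so 0/16.
- No Grade 4 hyponatremia in either table.
- Planned maximum: 20 patients (Section 14).

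Exact (Clopper-Pearson) 95% intervals: 8/50 gives 7.2% to 29.1%; 0/16 gives 0 to 20.6%.

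Expected cases in 20 = 20p, and chance of at least one = 1 - (1 - p)^20:

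| Rate p | Source | Expected in 20 | P(at least one) |
|---|---|---|---|
| 0 | AML point estimate | 0 | 0 |
| 0.05 | assumed, for illustration | 1.0 | 0.64 |
| 0.16 | solid-tumor point estimate | 3.2 | 0.97 |

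Over the intervals, the expected count is 0 to 4.1 from the AML data (20 × 0.206) and 1.4 to 5.8 from the solid-tumor data (20 × 0.072 and 20 × 0.291).

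The two sources cannot be clearly separated. If the true rate were 16%, the chance of none in 16 is 0.84^16 = 0.061, and Fisher's exact test of 8/50 against 0/16 gives p = 0.18.

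The Phase 1 report does not split its Grade 3 cases at a sodium of 125, so these counts cover both Grade 3 rows. The number in the 126-129 row alone would be the same or smaller.

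**How many doses per episode**

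Section 9.2 takes a patient off treatment if a drug-related delay exceeds 21 days, and a 21-day cycle contains 4 doses (Section 9.1.1). A hold that still allows a restart therefore affects at most about 4 doses.

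**The case against.** The strongest reply is that an exception is supposed to differ from the rule it qualifies. Section 9.2.5 says in terms that it is an exception, so a reader who infers that the protocol leaves precedence unstated would be wrong. This stands. The remaining problem is that the exception is wide enough to undo a specific safety row, with nothing to show that this was intended.

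The bullet does have a functional limit: sodium that stays low despite salt falls outside it, and Table 2 then applies. The wording is also permissive and obliges nobody to dose. Both points stand and reduce the risk, but reversibility is known only after the event, and a permissive waiver still makes Table 2's hold optional. The bullet may have been meant only for electrolytes without their own row. That is the most sensible reading, but the protocol does not state it.

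Existing safeguards also limit the effect. The Section 10 calendar schedules chemistry on days 1 and 14 from cycle 2, and Section 13 lets the investigator remove a patient the third time the same non-hematologic toxicity reaches Grade 3 or worse. A reader might infer from the calendar notes, which from cycle 2 require investigator review only of a CBC before the first dose, that chemistry is not seen before dosing. Section 9.1.1 does not support this: it allows a later start within a given cycle because day-1 laboratory results are needed. On the other side, the Principal Investigator consultation in Section 9.2.7 covers delays, modifications and reintroductions. Continuing unchanged is none of these.

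**Conclusion.** The point holds and is minor. Read literally, Section 9.2.5 overrides Table 2's hold for asymptomatic Grade 3 hyponatremia at 126-129 and, less plausibly, the more severe row. The practical effect is some doses given that Table 2 would have held, in about 0 to 3 of 20 patients. That range assumes that one or other Phase 1 rate carries over to MDS patients on 60 mg twice weekly, two weeks in three. Doses and schedules in those studies differed, so the figures show scale only. In the 126-129 row the restart dose is the same under both rules. Sample size, error rates, the primary endpoint and its decision rule are untouched.

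Two stronger readings should not be drawn:

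- *That the protocol lists Grade 3 hyponatremia as common.* Table 2 attaches that label to hyponatremia as a whole, and Section 11 lists low sodium without a grade in its band above 20 per 100. The Grade 3 point estimates, 16% and 0%, are both below that band.
- *That Section 9.2.5 treats Grade 3 diarrhea more leniently than Grade 2, for which Table 2 reduces the dose one level.* This comes from reading the heading, "Conditions Not Requiring Selinexor Dose Reduction", over the operative sentence, which waives only the hold. The bullet, "Grade 3 nausea, vomiting or diarrhea (unless persisting > 3 days with adequate treatment of anti-emetics or anti-diarrheals", has its own time limit, and Section 9.2.1 has a parallel three-day allowance for toxicity unrelated to selinexor, so the grace period looks deliberate. Whether to reduce during it is a clinical trade-off. The two Phase 1 tables show no Grade 3 diarrhea in 66 patients (50 + 16).

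**What to change.** In the electrolyte bullet of Section 9.2.5, insert after the opening reference to electrolyte abnormalities the clause: *other than hyponatremia (which is managed per Table 2)*. Leave the rest of the bullet unchanged. It then keeps its use for hypokalemia and similar events, and both Table 2 hyponatremia rows apply as written. A grade or sodium cap on the whole bullet is not needed to remove this conflict.

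The cost is one clause in an amendment and, if Grade 3 hyponatremia occurs, a few more held doses. No statistical section needs to change.
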